4.2 Secondary Subjects

NA

4.3 Number of Subjects

A. Total Number of Subjects

12/31/2499

Based on prior work by our group, we anticipate that approximately 25% of subjects who enroll in the study will withdraw/drop out early. Currently the study requires 45 people of 80 given it is a transfer project when our team was at the University of Virginia. In addition, we expect that 70% of individuals who we screen/consent will not qualify. **Thus, we expect to screen 225 subjects of whom about 67 will participate and 45 will complete the study.**

B. Total Number of Subjects If Multicenter Study

NA

C. Feasibility

We are confident that we can recruit the required number of health volunteers given the population in and surrounding Rutgers University. We are also confident we can recruit patients with risk factors for metabolic syndrome in the Clinical Academic Building at RWJMS.

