1.3 Research Design and Methods

This is a randomized by sex, double-blind, placebo controlled trial. People with metabolic syndrome will undergo exercise at low and high intensity with placebo, and this will serve as the control to the same exercise programs but with metformin. During this trial, subjects in the metformin group will receive only regular metformin, not metformin ER.

12/31/2499

A. Research Procedures

Note: All assessments outlined in this consent are being done for research purposes only. In light of COVID-19, we will follow routine safety checks per University guidelines until otherwise deemed unnecessary. These checks will be implemented at time of in person visits and consist of: temperature check and questions related to exposure yourself or to others with COVID-19. Face masks should also be worn unless otherwise indicated.

PHASE 1: SCREENING AND TESTING PROCEDURE

*Note: Portions of screening visits 1 and 2 can be combined to ease your burden and number of visits.

Screening Visit 1 at the Clinical Research Center (CRC) or Institute for Food, Nutrition and Health (IFNH) (Day 1) (will last about 1- 2 hours)

Prior to signing this consent, subjects were contacted by a member of the study following your interest in this study. If subjects agree to participate, subjects will sign this consent form before any study related procedures take place. Before subjects can start the study, there will be a screening period. Subjects will have tests and procedures during this time to make sure they are eligible, and it is safe for participation. Subjects are to fast (nothing to eat or drink after midnight) for blood work. Water is ok. These include the following:

- Health history and Physical Activity Readiness Questionnaire (PAR-Q) that will take about 30 minutes to complete
- Vital signs (blood pressure, heart rate)
- Subjects height, weight, and waist circumference will be measured.
- Blood draw will also be performed for laboratory testing.
- Subjects body mass index (BMI) will then be calculated. It must be between 25-47 kg/m² for you to be able to continue in this study.

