1.5 Sample Size Justification

The primary outcome for this study will be changes of basal flow mediated dilation (FMD) before the insulin clamp pre and post intervention. Based on our prior work 47, with 15 subjects per treatment arm we expect to have at least an 80% chance of rejecting the null hypothesis that the mean pre to post-exercise change in FMD is the same for any pair of treatments if the true means of the underlying distributions differ by more than 4.2%. Details: In computing the minimum detectable effect size of 4.2%, we assumed that the measurements for pre to post-treatment change in FMD will be normally distributed and that the measurement variability in the pre to postexercise FMD changes is the same regardless of the treatment. Moreover, we assumed that the standard deviation of the underlying distributions is 3.4% based on our prior work 47, which is notably larger than reported in the metformin literature 48. To account for a total of 6 pairwise between-treatment comparisons, a Bonferroni corrected experiment-wise type I error of 0.05 was utilized to derive the minimum detectable between-treatment difference of 4.2%. Limitations: We do not have data from the literature or from our own studies with exercise to estimate power on changes in MBV, nor with the combination of exercise+metformin. However, considering MBV, we based our estimate of sample size on our study examining the effect of insulin on MBV in both skeletal and cardiac muscle in the control setting and in the setting of elevated plasma FFA. We observed that insulin significantly increased microvascular blood volume (MBV) at both sites (p<0.01) in the absence of elevated FFA and this effect was entirely blocked by elevating plasma FFA. These observations were made in 22 subjects, although less would have yielded significance ^{36, 42}. Moreover, previous work that we conducted with HiEx+metformin demonstrated significant blunting effects on systolic blood pressure vs. exercise alone with only 8 people per group 5. Anticipated dropout: Based on our prior work with this study population, we anticipate that the study participant dropout rate will be 10-15%. Therefore, we intend to enroll 80 subjects with 20 subjects randomized to each treatment intervention.

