1.6 Study Variables

A. Independent Variables, Interventions, or Predictor Variables

This is a randomized by sex, double-blind, placebo controlled trial. A placebo is needed to minimize potential behavioral changes with pharmacological intervention. This will isolate the effects of exercise intensity based training on respective outcomes. As a result, exercise at low or high intensity with placebo will serve as standard of care/control, while exercise at low or high intensity with metformin will be the experimental conditions. Pre and post test data will be compared statistically.

Data will be analyzed using R (Vienna, Austria, 2011). A two-way repeated measures analysis of variance (ANOVA) will be used to assess time course differences (group x test). Bonferonni post-hoc analysis will be used to determine group differences and paired t-tests will be used to assess within treatment effects. Linear regression analyses will be used to identify relationships between respective variables. A *P*<0.05 will be considered statistically significant. Data will be expressed as mean ± SEM.

12/31/2499

The same statistical approach for secondary analysis will be conducted as the primary variable analysis.

B. Dependent Variables or Outcome Measures

- 1. Insulin Sensitivity
- 2. Fitness (e.g. VO2max, physical activity amount, heart rate, RPE, etc.)
- 3. Body composition (e.g. weight, fat, FFM, BMD, waist circumference, etc.)
- 4. Vascular Function (e.g. FMD, CEU, heart, arterial stiffness, etc.)
- 5. Questionnaires (e.g. Sleep, activity, quality of life, hunger, etc.)
- 6. Glucose (e.g. substrate, isotope)
- 7. Lipid Profile (e.g. TG. HDL. FFA. etc.)
- 8. Blood clinical chemistries (e.g. CBC)
- 9. C-peptide
- 10. Insulin
- 11. Inflammation (e.g. endothelin-1, adiponectin, Microparticles, etc.)
- 12. Nitrates
- 13. Gut hormones (e.g. ghrelin, GLP-1, etc.)
- 14. Pregnancy (in females), blood for screening at each admission.
- 15. Energy metabolism (e.g. rest, exercise, insulin-stimulation).
- 16. Gut microbiota
- 17. Cognitive measures using NIH toolbox

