2.4 Research Sites

All research will be conducted at Rutgers (e.g. Loree, IFNH and/or CRC) as described.

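### Section 4.3 implies that a previous university contributed participants, yet the only analysis model has no site term, so any site difference in FMD change stays in the error

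*Combined protocol and SAP*

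**What the plan says.** **Transfer and counts.** Section 4.3 A states: "Currently the study requires 45 people of 80 given it is a transfer project when our team was at the University of Virginia". It continues: "Thus, we expect to screen 225 subjects of whom about 67 will participate and 45 will complete the study". Behind that projection are two rates: "we expect that 70% of individuals who we screen/consent will not qualify", and "approximately 25% of subjects who enroll in the study will withdraw/drop out early". Section 1.5 plans on 15 per arm for power and 80 enrolled, 20 per arm, with a lower loss: "we anticipate that the study participant dropout rate will be 10-15" per cent.

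**Site.** Section 2.4 reads: "All research will be conducted at Rutgers (e.g. Loree, IFNH and/or CRC) as described". Section 3.0 (multi-center research) and section 4.3 B (multicenter numbers) are both answered NA.

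**Randomisation.** Section 1.3 says: "This is a randomized by sex, double-blind, placebo controlled trial". Section 1.6 repeats this. Sex is the only factor named.

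**Analysis.** Section 1.6 gives the model: "A two-way repeated measures analysis of variance (ANOVA) will be used to assess time course differences (group x test"). Bonferroni post-hoc comparisons follow, and the same approach is used for secondary outcomes. Section 6.1 (Data Analysis) holds only the template prompt, so it adds no further model.

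No section available for review says how the earlier participants' data are combined with the new data, whether the allocation list was continued or restarted after the move, or how FMD and clamp measurements are kept comparable between the two places.

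**The concern.** The primary outcome is the change in basal FMD, an ultrasound measure, over a 16-week supervised training programme. A move between universities can change the laboratory, device, operators and training facility. Section 1.3 also allows virtual training sessions if COVID-19 makes them necessary, so training delivery may differ by period. If the average FMD change differs between the two places for any such reason, a model with only group and test treats that difference as noise.

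What is at stake is the precision of the six pairwise arm comparisons, in a trial with no spare power (see the working). Site is fixed before randomisation and already known for every participant, so the loss can be avoided at almost no cost.

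**Working it through.** **1. How large is the earlier-site share?** The documents do not state it. Three readings of section 4.3 are possible:
- Both counts are on the same basis: 80 − 45 = 35, and 35/80 = 44%.
- The 67 are new enrolments added to 35 earlier ones: 35/(35 + 67) = 34%.
- The 45 are completers, set against 4 × 15 = 60 planned completers: 60 − 45 = 15, and 15/60 = 25%.

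The projection does not settle which applies. 225 × 0.30 = 67.5 agrees with about 67 participating, but 67 × 0.75 = 50, not 45; 45 of 67 implies a 33% loss.

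**2. The plan's own power figure.** Inputs from section 1.5: difference 4.2, SD 3.4, 15 per arm, 0.05 shared over 6 pairs (0.00833 each). Sidedness is not stated; two-sided is assumed. On the normal approximation, power = Φ(4.2 / (SD × √(2/15)) − 2.638).

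With SD 3.4 this is Φ(3.383 − 2.638) = 77.2%, against a stated minimum of 80%. The formula gives 16 per arm for 80% and a detectable difference of 4.32 at 15 per arm. This is close to the plan's 15 and 4.2, and 77.2% is the baseline below. An ANOVA t calculation with 56 degrees of freedom gives 73.9%; a one-sided test gives 83.9%.

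**3. Cost of leaving site out.** Let p be the earlier-site share and D the difference between sites in mean FMD change. D is an assumption, and 3.4 is taken as the within-site SD. The variance added is p(1 − p)D², so SD = √(3.4² + p(1 − p)D²). For p = 35/80, p(1 − p) = 0.246 and 3.4² = 11.56. With D = 2, for example, 0.984/11.56 = 8.5%.

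Each cell gives added variance; SD; power at 15 per arm:

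| Share p | D = 1 | D = 2 | D = 3 |
|---|---|---|---|
| 35/80 (44%) | 2.1%; 3.44; 76.1% | 8.5%; 3.54; 72.9% | 19.2%; 3.71; 67.8% |
| 35/102 (34%) | 1.9%; 3.43; 76.2% | 7.8%; 3.53; 73.2% | 17.5%; 3.69; 68.5% |
| 15/60 (25%) | 1.6%; 3.43; 76.4% | 6.5%; 3.51; 73.9% | 14.6%; 3.64; 69.9% |

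With the right site term the SD returns to 3.4 and power to 77.2%.

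**4. Which term removes it?** In a group by test model the contrast of interest is the within-person change. A site main effect adds the same amount to both measurements and drops out of that change, so it leaves the group by test error as it was. A simulation of 80 participants with D = 3 gave these change-scale residual variances:
- no site term: 12.86
- site main effect only: 12.86
- site × test added: 10.87

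Site as a factor in a model of change scores is equivalent to site × test.

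**5. Is imbalance of site between arms a further harm?** With 35 of 80 from the earlier site, 20 per arm and allocation at random with respect to site, the 95th percentile of the difference in site share between two given arms is 0.30. That shifts their contrast by 0.3, 0.6 or 0.9 points for D = 1, 2 or 3. Over repeated allocations, this shift has variance 0.025, 0.10 and 0.22. The variance that step 3 adds to a contrast of two arms of 20 is 2p(1 − p)D²/20 = 0.025, 0.098 and 0.221. The two agree, so it is one effect and should be counted once.

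**The case against.** **The effect may be small.** A constant difference in scanner, operator or facility affects the measurements before and after training alike and cancels. Only a site difference in change matters, and the documents give no figure for one. At 1 point, power moves by about one percentage point. The virtual sessions are conditional. All of this stands: the point is about precision, and it is modest unless the site difference in change is about 2 points or more.

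**A reader might infer that the between-arm contrasts are biased.** The documents do not support that. Under random allocation, chance imbalance of site is part of the same loss of precision (step 5). Bias would need allocation to differ systematically by site, and nothing in the text shows this. Nor is blocking described; blocked or restarted allocation would make the imbalances smaller than in step 5.

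**A reader might take 35 of 80 as a stated fact.** It is a subtraction that may mix enrolled and completed participants, hence the 25% to 44% range.

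**A reader might say that the protocol declares itself single-site.** It does not use those words. Section 2.4 looks forward, the NA answers respond to template headings, and a study that moves need not be concurrent multi-center research. Section 4.3 also discloses the transfer. What remains is that section 2.4 read alone gives no sign of the participants implied by section 4.3, and the analysis makes no provision for them.

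**Conclusion.** The point holds as a precision and reporting problem that should be corrected. Section 4.3 implies that between a quarter and 44% of participants were obtained at a previous university, and neither the primary nor the secondary model accounts for it. For assumed site differences in FMD change of 1 to 3 points, the variance rises by about 2% to 19% at the 35:45 split, and power falls from 77% to between 76% and 68%. At the 25% share the fall is to between 76% and 70%.

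These figures rest on the assumed differences, on 3.4 being the within-site SD, on two-sided testing at 0.00833 per pair, and on the normal approximation. The conclusion that site belongs in the model does not depend on the exact share.

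**What to change.** 1. In the primary and secondary models, include site (previous university or Rutgers) and site × test, together with sex, the stated randomisation factor, and sex × test. Equivalently, use site and sex as factors in a change-score model. A site main effect alone in the repeated-measures model is not enough.
2. Reconcile sections 2.4, 3.0 and 4.3: state the numbers randomised and completed at each site by arm, and say what the 45 and the 80 count.
3. State whether the allocation list was continued or restarted, and balance the remaining randomisation by sex within the current site. Do not fix the number still to be randomised at 45, since section 4.3 expects about 67 to participate and 45 to complete.
4. Optionally, add a site-by-arm analysis as a sensitivity analysis, labelled as low-powered; it uses 3 further degrees of freedom.

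The cost is one degree of freedom for site and one for sex in the change analysis, plus wording. On the ANOVA t calculation at 15 per arm, the degree of freedom for site leaves the detectable difference at 4.46 (56 against 55 degrees of freedom). No new data or participants are needed. The change is most credible if made before unblinding.

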4.4 Consent Procedures

A. Consent Process

Location of Consent Process

The Clinical Research Center at the Robert Wood John Medical School, Institute for Food Nutrition, and Health or Loree Gymnasium in New Brunswick NJ 08901. Consent process will take place in a private room.

Ongoing Consent

NA

Individual Roles for Researchers Involved in Consent

Principal investigator, [name], and study team members, e.g. [name], [name], etc. will inform and answer questions of potential participants of all aspects of the study during the consent discussion. Another member from the lab will conduct the consent discussion is neither the principal investigator nor study coordinator are available. [name], or [name]/ etc. will sign the consent form.

Consent Discussion Duration

Consent process is expected to last 60 minutes.

Coercion or Undue Influence

To minimize the possibility of coercion or undue influence, the consent discussion will not be conducted by laboratory staff who have any known relationship with prospective participants. Individuals will be made aware it is his/her choice whether to take part in the research his/her relationship with the study staff will not change, and he/she may do so without penalty and without loss of benefits to which he/she is otherwise entitled. Participants will also be provided consent forms prior to meeting to allow appropriate decisions without pressure.

Subject Understanding

Subjects will be made aware of the risks associated with blood draws and the number of blood samples requested during each test day. Subjects will also be made aware of side effects associated with exercise, metformin and research tests. Potential participants will be encouraged to ask questions and be asked questions by staff conducting the consent process to ensure understanding of the study.

B. Waiver or Alteration of Consent Process

Waiver or Alteration Details

12/31/2499

NA

Destruction of Identifiers

NA

Use of Deception/Concealment

NA

a. Minimal Risk Justification

NA

b. Alternatives

NA

c. Subject Debriefing

NA

UPLOAD to e-IRB Section 13.17 Consent Form - The consent form(s) you plan to use to inform and consent individuals to take part in the research.

C. Documentation of Consent

Documenting Consent

Please see consent form attached. The research team will verbally read the consent form with the potential subjects. During this time, all questions will be answered as to increase the participants' comprehension and understanding of the study. The research team and participant will sign the consent prior to any tests. Subjects will receive copies of the consent.

 Waiver of Documentation Of Consent (i.e., will not obtain subject's signature) NA

4.5 Special Consent/Populations

- A. Minors-Subjects Who Are Not Yet Adults
 - Parental Permission

NΑ

Non-Parental Permission

NA

Assent Process

NA

Documentation of Assent

NA

Reaching Age of Majority During Study

NA

B. Wards of the State

 Research Outside of NJ Involving Minors NA

C. Non-English-Speaking Subjects

12/31/2499

- Process for Non-English-Speaking Subjects
 We will not be recruiting non-English speaking individuals.
- Short Form Consent for Non-English Speakers NA

D. Adults Unable to Consent / Decisionally Impaired Adults

- NJ Law-Assessment of Regaining the Capacity to Consent NA
- Capacity to Consent
 - a. NJ Law-Selecting A Witness
 - b. Removing a Subject NA

4.6 Economic Burden and/or Compensation for Subjects

A. Expenses

There are no expenses incurred by the subject taking part in the research and therefore no reimbursement will be given. We will validate parking at the Robert Wood Johnson University Hospital parking deck for those that may need it. Subjects may lose compensation from their own jobs if they miss work for screening and experimental visits. However, this is a voluntary study and subjects will not be reimbursed for lost wages.

B. Compensation/Incentives

Incentives for this study will be a check for successful completion of protocols at set times (see consent form), food before/after test days and supervised exercise sessions in addition to a heart rate monitor used in the study.

Option 1:

Completion of Phase 3: \$200
Completion of Phase 3(with isotope): \$300
Completion of Phase 4: \$600
Completion of Phase 4 (with isotope): \$700
Completion of Visit 57: \$200
Completion of Visit 58: \$300

Total payment: \$1,300 (without isotope) or \$1500 (with isotope)

Option 2:

(Without isotope) Completion of Phase 3, Phase 4, Visit 57 and Visit 58 (With isotope) Completion of Phase 3, Phase 4, Visit 57 and Visit 58 \$1,300

C. Compensation Documentation

Subjects will be compensated with a check processed through RU Marketplace. Subjects will have the option to receive compensation either at specified time points during the study or a total sum at the end of the study. Research team members will collect information including name, address,

12/31/1799

12/31/2499

Approval Date:

^{*}Will be able to keep Polar HR monitor at the end of the study. (~\$150)

^{*}Will be able to keep Polar HR monitor at the end of the study. (~\$150)

telephone number, DOB and social security number to fill out the necessary forms through Rutgers University.

4.7 Risks of Harm/Potential for Benefits to Subjects

A. Description of Risks of Harm to Subjects

Reasonably Foreseeable Risks of Harm

Fitness tests may cause anxiety and/or claustrophobia due to mouthpiece or canopy from indirect calorimetry. Cardiovascular reactions to exercise could include fainting, syncope, chest pain or sudden cardiac death. The later though occurs rarely (risk of cardiac events during exercise testing: 3/5,000 tests; risk of death during exercise: ~1/18,000 individuals per year).

During FMD, subjects may experience mild discomfort (e.g. mild pain, tingling, and/or numbness) in their forearm and/or hand as a result of the prolonged inflation (5 min.) of the blood pressure cuff required for the procedure. This occurs rarely.

IV catheter insertion risk are minimal but could include hematoma, venous thrombosis or infection at the IV site. Subjects may, although rare, feel fain during venipuncture. Also minimal, the risk of isotope tracers include infusion and allergic reaction. Signs and symptoms of such reactions may include low blood pressure, fast heart rate, rash, vomiting, fever, chills, flushing or nausea. Subjects do not need to take any precautionary safety measures before or after infusions. There is no radioactive energy emitted, as they do not spontaneously decay.

Metformin side effects, such as diarrhea, nausea, upset stomach, and abdominal pain may occur. Hypoglycemia is also possible and feelings may include: fatigue, lightheadedness, mood changes, hunger, clammy hands and/or feet. Metallic taste and lactic acidosis also may occur, but are rate. Minimized by following a ramp up protocol over 4 weeks t gradually acclimate the subject. Recommendation ingestion with food will also minimize side effects of low blood glucose and avoiding alcohol intake during the study. People with history of renal/congestive heart failure/liver disease will be excluded to also minimize risk of lactic acidosis, which occurs in ~1/33,000 patients per year).

Definity Microbubbles side effects include: headache, back and chest pain, flushing, dizziness, a metallic taste, vomiting, coughing, and dry mouth. The FDA has issued a black box warning for Definity (a type of warning that appears on the package insert for certain drugs that may cause serious harmful effects) for cardiopulmonary and hypersensitivity reactions. There have been convulsions, arrhythmias, respiratory distress, and death noted in patients with an intracardiac or intrapulmonary shunt so the FDA has suggested using it with extreme caution in patients with known cardiac or cardiopulmonary disease. We will not have any of these types of subjects in our study but should an emergency arise we will have trained personnel and resuscitation equipment available. We have been using Definity in subjects with obesity for over 4 years (~ 100 subjects) and we have had 0 adverse events. Thus, these occur rarely.

Insulin infusion: There is a potential for hypoglycemia (not very often). The doses of insulin used during the euglycemic insulin clamp are low and the blood glucose level will be monitored every five minutes throughout the insulin infusion. The glucose infusion will be adjusted to maintain the subject's glucose level within 10% of normal fasting. This occurs infrequently.

Body composition: Air displacement determination of body composition by Bod Pod may cause anxiety and /or claustrophobia. The DXA measurements will produce a small amount of radiation which is less than that received during two days of background radiation.

12/31/2499

A subject may incur lost wages from his/her job due to time spent at the screening and/or experimental visits. There is also the possibility, though low, for breach of confidentiality with using an outside company, Greenphire, to distribute the ClinCard compensation.

Risk of Harm from an Intervention on a Subject with an Existing Condition

We expect our subjects to be generally healthy and should not have any severe or decompensated medical conditions. Exclusion criteria and physicals performed should minimize any risks and the exercise/metformin treatment should not bring harm.

Other Foreseeable Risks of Harm

We do not anticipate any other foreseeable risks given the scope and duration of the study.

 Observation and Sensitive Information NA

B. Procedures which Risk Harm to Embryo, Fetus, and/or Pregnant Subjects

Pregnancy is an exclusion criterion, and women of childbearing age will undergo a bedside urine pregnancy test prior to treatment.

C. Risks of Harm to Non-Subjects

NA.

D. Assessment of Social Behavior Considerations

Questionnaires used in this study do not assess depression or suicidal ideations. As a result, we do not anticipate these assessments.

E. Minimizing Risks of Harm

All efforts will be made to minimize risk.

General Efforts

- A careful history and physical examination to exclude those subjects with a history or current symptoms of cardio-pulmonary conditions as well as renal, liver or metabolic disease.
- CBC with differential to screen out people with low hematocrit or evidence of infection or other illness
- Glucose and HbA1c to screen undiagnosed diabetes
- Pregnancy test in females
- Liver, kidney, and hematologic function will be assessed from blood samples using standard clinical tests listed below:
 - o CBC, eGFR, and creatinine, tests within normal limits
 - o Liver function tests no greater than 2-fold within normal limits
 - HCT for women > 36%, Men >38%
- Complications of IV will be minimized by aseptic and skilled techniques
- Each exercise test will be monitored by researchers on the IRB protocol or CRC personnel who
 have current training in CPR and AED use. An AED and a cell phone available to call 911 if
 necessary. While a physician is not required to be present during exercise testing in this population
 (according to AHA/ACC/ACSM guidelines), it is standard CRC/medical practice that the study
 physician is aware of the test and available by page.

12/31/2499

- If a subject develops leg pain during the exercise treadmill test, the speed/incline on the device will be decreased.
- Fitness testing, DEXA as well as IV placement will be performed by trained personnel

Conditions whereby a subject's participation or study treatment may be stopped or modified:

- If subject has any of the less likely to severe side effects for a particular admission that study will be terminated and depending on the side effect as well as extent may be excluded from all admissions.
- Any significant blood loss is prevented by regular visual inspection of the catheter insertion site and removing a catheter and applying pressure if there is obvious extravasation of blood into the tissue.
- These catheters are in place for a brief time (~5 hours) and careful aseptic technique is used for catheter placement. With these precautions infections secondary to intravenous lines is extremely uncommon. Should an infection occur, we would treat with oral or intravenous antibiotics or if necessary, by local drainage.
- If the subject experiences headache, chest pain, vomiting, flushing, or dizziness.
- If the subject experiences hypoglycemia with a blood glucose of 60 or less the study will be stopped.
 It may be stopped at a higher value at the discretion of the Principal Investigator if there is loss of IV access.
- A woman with a positive pregnancy test will be excluded.

Exercise Testing (VO2max test)

The ACC/AHA guideline update for exercise testing endorsed by the American College of Sports Medicine (ACSM) is used in the Clinical Research Center and IFNH for all exercise protocols. This document provides guidelines for absolute and relative indications for terminating exercise testing. In addition to [name] and [name], [name], the Director of Cardiac Non-Invasive Laboratories and cardiologist, will serve as reference for interpreting ECG work and verify safety in exercise training.

Exercise Termination:

Absolute

- 1. Drop in systolic blood pressure of >10 mm Hg from baseline blood pressure despite an increase in workload, when accompanied by other evidence of ischemia
- 2. Moderate to severe angina
- 3. Increasing nervous system symptoms (e.g. ataxia, dizziness, or near syncope)
- 4. Signs of poor perfusion (cyanosis or pallor)
- 5. Technical difficulties monitoring the ECG or systolic blood pressure
- 6. Subject's desire to stop
- 7. Sustained ventricular tachycardia
- 8. ST elevation (>1.0 mm) in leads without diagnostic Q-waves other than V1 or aVR.

Relative

- 1. Drop in systolic blood pressure of >10 mm Hg from baseline blood pressure despite an increase in workload, in the absence of other evidence of ischemia.
- 2. ST or QRS changes such as excessive ST depression (>2mm horizontal or down-sloping ST-segment depression) or marked axis shift

12/31/2499

- 3. Arrhythmias other than sustained ventricular tachycardia, including multifocal PVC's triplets of PVC's, supraventricular tachycardia, heart block, or bradyarrhythmias.
- 4. Fatigue, shortness of breath, wheezing, leg cramps, or claudication
- 5. Development of bundle-branch block or intraventricular conduction delay that cannot be distinguished from ventricular tachycardia
- 6. Increasing chest pain
- 7. Hypertensive response: systolic >250 mm Hg, diastolic >115 mm Hg.

Metformin Treatment

- 1. People will follow up a 500 mg/d ramp up protocol until 2000 mg/d is met (expected week 4.
- 2. In the event someone is not able to tolerate a dose, people will be held at that dose for approximately 1 week, thereby increasing the dose at a level tolerable to the subject.

Blood draws

Total of approximately 368 (8 cc, 155 cc x 2 (pre and post test) + 50 cc (follow-up)) cc of blood will be collected during the entire study and tested for:

- 1. Glucose (e.g. substrate, isotope)
- 2. Lipid Profile (e.g. TG, HDL, FFA, etc.)
- 3. Blood chemistries
- 4. C-peptide
- 5. Insulin
- 6. Inflammation (e.g. endothelin-1, adiponectin, Microparticles, etc.)
- 7. Nitrates
- 8. Gut hormones (e.g. ghrelin, GLP-1, etc.)

Subjects will be advised to not donate blood during the study to minimize risk of anemia.

Clamp Protocol

With each study protocol there will be documentation of study records of drug administration and the person who administers. For microbubbles, isotope and insulin, administration is always intravenous. All invasive training protocols are under supervision of an MD. However, an MD will not be required to be present in the room when performing them, as all research personnel (e.g. [name], [name]) are trained to implement the protocol and will be under the supervision of the MD.

[name] and [name] will serve as primary endocrinologists on the study. [name] and [name] have reviewed and approved all aspects of monitoring patient safety, drug preparation and administration (including preparation of infusates for insulin clamp studies and administration of Definity microbubbles for microvascular imaging). The team has written protocols for preparation and administration of pharmaceuticals, which are prepared by [name], a pharmacist in the CRC.

The team is aware how to treat adverse events, should they arise. Potential adverse events include: 1) hyper or hypoglycemia secondary to infusion of either glucose or insulin; 2) back pain secondary to infusion of microbubbles which is treated by discontinuing the infusion and resolves spontaneously in 3-5 minutes; 3) idiosyncratic reactions (e.g. vasovagal syncope from phlebotomy or venipuncture) which is treated with supine posture, cold compresses and if necessary saline infusion; 4) allergic reactions which is treated by stopping all infusions, administering Benadryl if needed. In the event of any of the above, either [name] or another designated licensed practitioner on the IRB protocol will be available for immediate consultation.

Emergency Response in CRC

The CRC has stock medications on site for emergency use (i.e. diphenyhydramine, Epipen), as well as IV fluids and oxygen. An AED is located in the hallway outside of the CRC. If a subject becomes unresponsive or hypotensive, nursing and other staff will be summoned to the study area for immediate assessment. If the subject is thought to be having a severe allergic reaction and/or is hypotensive, any study infusions will

12/31/2499

be stopped, and treatments will be administered either per a licensed MD present in the room during the procedure or according to the established CRU standing order for an allergic reaction. This will include the use of IV fluids, Epipen, diphenyhydramine and oxygen as applicable. Other personnel will immediately call the RWJMS Emergency Services line [contact]) and call the study physician if not already in the room.

Certificate of Confidentiality

This study is funded by NIH RO1 5R01HL130296 and a Certificate of Confidentiality was automatically issued.

Provisions to Protect the Privacy Interests of Subjects

Subjects will only interact with research team members. If a subject does not feel comfortable sharing personal health information, she/he does not need to participate in the study.

All research records are kept strictly confidential and in a locked cabinet and a locked computer that requires a password; which is available only to persons conducting the study and who have passed the Human Certification (CITI) training. Samples sent to the laboratory (screening/analytes for analysis) do not have any names on them and are only identified with ID #code. The de-identified blood and urine samples are kept in a locked freezer, and the cabinets, computers and freezers are within the principle investigator's oversight to ensure participant confidentiality.

F. Potential Benefits to Subjects

There will be no immediate benefits from participation in this study. The procedures done for this study are investigational and have no immediate health benefits.

